7.3.3. Treatment Compliance

On the date of the first dose of study medication, the patient is expected to take only one dose (3 tablets) of study medication (in the evening). For the remainder of the study, patients should take two doses (6 tablets) of study medication each day (one in the morning and one in the evening).

At designated visits (i.e. Weeks 1, 3, 5, 9, 13, 17, 21, 26, 30, 34, 38, 42 and 46) patients will be distributed bottles containing study medication. Patients will return the bottles at a subsequent study visit, as instructed.

The number of tablets taken will be derived as: (total tablets dispensed across visits – total tablets returned across visits) and will be used to assess overall study compliance.

The total number of tablets planned will be derived as:
 $3 + (\text{number of days between day after first dosing day and last dosing day, inclusive}) * 6$.

Patient compliance over the entire time interval from first day of treatment until the last reported dosing date will be derived as: $(\text{number of tablets taken}/\text{number of tablets planned}) * 100\%$. Patient study compliance will be summarized using descriptive statistics overall for the safety population.

Patient compliance information will be presented in a data listing for the safety population.

8. Secondary Endpoint Analysis

Efficacy measurements will be evaluated as secondary endpoints in this study. The safety population will be used to evaluate the efficacy endpoints defined for this study. Eligibility for analysis of a particular endpoint will require only that the patient have a baseline value and at least one post-baseline value so that a change from baseline calculation can be obtained. All efficacy endpoints will be evaluated through the generation of descriptive summary statistics. For continuous variables, the mean, standard deviation, median, minimum, and maximum will be presented for a particular visit and for the change from baseline (Visit 1a or 1b). For categorical variables, the number and percentage of patients within each category of classification will be summarized by study visit. No formal statistical testing will be conducted.

Visit 1a or 1b will serve as the baseline visit for efficacy endpoints. Visit 1a will be the baseline for patients directly entering the Treatment Period as of Visit 1a and Visit 1b will be the baseline for patients entering the Treatment Period after participating in the Observation Period for any length of time.

Last observed value (LOV) is defined as the values at the last post-baseline visit, up to and including the Safety and Washout Period visit.

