3.4. Treatments

Following enrollment, the patient will receive 30 mg open-label tablets. At each visit at which study drug is to be dispensed, enough drug should be supplied to ensure a sufficient number of tablets available for dosing until the next visit plus an additional 8 tablets to allow for visit windows and/or possibility of a missed visit.

Study drug can be taken with or without food. Patients will be instructed to take the AM and PM Study Drug tablets at the same times of the day, approximately 12 hours apart, preferably with 240 milliliters (mL) (approximately 8 ounces) of water. If the patient does not take a particular dose at the planned time he or she may take it up to 2 hours later. For example, if a patient is taking the Study Drug at 9 AM and 9 PM but forgets to take the 9 AM dose, the patient may take the 9 AM dose as late as 11 AM. After that time, the patient should skip the 9 AM dose and, instead, take the regularly scheduled next dose at 9 PM.

The first dosing day will be on either Visit 1a or Visit 1b. Titration will be based on tolerability. If the patient is experiencing a study-drug related AE or an AE that may be aggravated by study drug up-titration, the study drug dose should not be increased, regardless of the NRS score.

The Study Drug will be titrated during the Treatment Period Weeks 1 - 4, according to the schedule in Table 3 in the study protocol to a final dose of 30 mg BID up to 180 mg BID. The dosing for Treatment Week 1 is further described in Section 9.6.1 (Visit 1a) and Section 9.6.4 (Visit 1b) of the study protocol. Patients should only ever be dispensed a single strength of the study drug (e.g. 30 mg bottle(s) or 60 mg bottle(s)) at a visit.

Patients will titrate to tolerability beginning with a 30 mg dose on Day 1 (Visit 1a or Visit 1b) with a dose increase of 30 mg BID not more often than every 3 to 4 days in order to attain steady-state plasma concentrations of nalbuphine at each dose.

Patients should be instructed to up-titrate beginning with a single 30 mg dose in the evening (PM) and then begin dosing with an increased 30 mg BID dose the following day. Dose titrations should be maintained for 3-4 days before further up-titration of the patient's dose is attempted

The maximum dose the patient should reach at the end of Week 1 is 60 mg BID. If this dose is tolerated (as determined by the Telephone Contact 1 (TC1) assessment), an additional up-titration may be attempted during Week 2.

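### The compliance formula assumes three tablets per dose for everyone, although dose and tablet strength vary by patient: perfect intake at 30 mg BID always scores 33%

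*SAP*

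**What the plan says.** Section 7.3.3 sets the planned intake in tablets, identically for all patients. On the first day, "the patient is expected to take only one dose (3 tablets) of study medication (in the evening"). From then on, "patients should take two doses (6 tablets) of study medication each day (one in the morning and one in the evening"). Planned tablets are 3 plus 6 times the "number of days between day after first dosing day and last dosing day, inclusive". The numerator is also a plain tablet count: "The number of tablets taken will be derived as: (total tablets dispensed across visits" less tablets returned). Compliance is taken over planned, times 100, summarised for the whole safety population and listed by patient.

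Section 3.4 describes a different regimen. "Following enrollment, the patient will receive 30 mg open-label tablets". Day 1 is a 30 mg dose. Dose then rises in 30 mg BID steps according to tolerance, with ceilings of 60, 120 and 180 mg BID at the ends of Weeks 1, 2 and 3. The dose reached by the end of Week 4 is kept as the maintenance dose, which may lie anywhere from 30 to 180 mg BID. Only one strength is dispensed at a visit, with 30 mg and 60 mg bottles given as the examples. Two dose reductions or holds per patient are allowed before the Medical Monitor has to be contacted.

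**The concern.** The two sections cannot both describe the same patient, except at particular combinations of dose and strength. A 30 mg first dose from 30 mg tablets is one tablet, not three, so the day-1 term is wrong for everyone. The later term is wrong wherever dose divided by strength is not three.

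Dose in this study is set by tolerance, so the error follows tolerability. Patients kept at 30 mg BID because they tolerate the drug poorly would be listed as one-third compliant with perfect intake. Patients on more than three tablets per dose could miss many of them and still look fully compliant.

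No other planned summary fills the gap. Missed doses are only listed (Section 7.3.1), exposure duration ignores missed doses and interruptions (Section 7.3.2), and Section 4.11 replaces the protocol's mean-dose summary with highest dose achieved. Section 1 gives the SAP precedence over the protocol on statistical analysis, so a better formula in the protocol would be overridden.

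**Working it through.** **Planned tablets as the SAP defines them.** Fifty weeks of treatment is 50 × 7 = 350 days. Planned = 3 + 6 × 349 = 2097. This follows correctly from the text of Section 7.3.3. The mismatch appears only when it is set against the dosing in Section 3.4.

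**Tablets per dose = dose ÷ strength.**

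| Dose (BID) | 30 mg tablets | 60 mg tablets |
|---|---|---|
| 30 mg | 1 | not possible |
| 60 mg | 2 | 1 |
| 90 mg | 3 | not possible |
| 120 mg | 4 | 2 |
| 150 mg | 5 | not possible |
| 180 mg | 6 | 3 |

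Three tablets occurs twice: 90 mg on 30 mg tablets and 180 mg on 60 mg tablets.

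**30 mg BID, perfect intake.** With n days after day 1, taken = 1 + 2n and planned = 3 + 6n = 3(1 + 2n). The ratio is 1/3 for every n. At 350 days it is 699/2097 = 33.3%. No assumption about duration or strength is needed.

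**Other maintenance doses, perfect intake over 350 days.** Assumed path: one 30 mg tablet on day 1, then BID, with 30 mg steps on day 4 or 5, day 8, day 11 or 12, day 15, and day 18 or 19, stopping at the maintenance dose. This respects the weekly ceilings. The SAP gives no date for a change to 60 mg tablets, so two are assumed: Week 5 (day 29) and Week 3 (day 15). For 180 mg BID with the Week 3 change, a single step from 120 to 180 mg between days 15 and 21 is assumed.

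| Maintenance dose (BID) | 30 mg tablets throughout | 60 mg tablets from Week 5 | 60 mg tablets from Week 3 |
|---|---|---|---|
| 60 mg | 1391–1393 (66.3–66.4%) | 747–749 (35.6–35.7%) | 719–721 (34.3–34.4%) |
| 90 mg | 2077–2079 (99.0–99.1%) | – | – |
| 120 mg | 2755–2759 (131.4–131.6%) | 1467–1471 (70.0–70.1%) | 1411–1415 (67.3–67.5%) |
| 180 mg | 4091–4097 (195.1–195.4%) | 2159–2165 (103.0–103.2%) | 2071–2087 (98.8–99.5%) |

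Example for 120 mg on 30 mg tablets with the earlier step days: 1 (day 1) + 2 × 2 (days 2–3) + 4 × 4 (days 4–7) + 3 × 6 (days 8–10) + 340 × 8 (days 11–350) = 2759, and 2759/2097 = 131.6%.

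**Sensitivity to the path.** Going from 120 mg directly to 180 mg on day 18, without a 150 mg step, gives 4087 tablets (194.9%) on 30 mg tablets throughout and 2155 (102.8%) with the Week 5 change. The single evening dose that starts each increase adds at most 5 tablets, 5/2097 = 0.24 points.

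**Masked non-adherence.** At 120 mg BID on 30 mg tablets throughout, a patient scores 100% after taking 2097 of 2755–2759 tablets. The share missed is 1 − 2097/2755 = 23.9% to 1 − 2097/2759 = 24.0%.

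**Dose holds.** Planned tablets accrue on every calendar day to the last dose, 6 per held day. An assumed 14-day hold adds 14 × 6 = 84, and 84/2097 = 4.0 points for a patient on three tablets per dose.

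**The case against.** The strongest reply is that the formula may be nearly right for the patients who matter most. Titration continues upward while tolerated, 180 mg BID is the ceiling, and at that dose on 60 mg tablets the score is about 99% to 103%. The 33% figure belongs to patients who never leave 30 mg BID, and the SAP does not say how many there will be. The figures above 130% need 30 mg tablets throughout, that is 8 or 12 tablets a day at 120 or 180 mg BID. Section 3.4 names 60 mg bottles and refers to a protocol titration table that is not at hand. The two strengths are also given only as examples.

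Most of this stands as a limit on size. The effect on the overall summary cannot be computed, and all figures other than the 33.3% are illustrations under stated assumptions. It does not rescue the formula: Section 3.4 allows maintenance at 30 mg BID, Section 7.3.1 plans to tabulate doses from 30 to 210 mg BID, and at 60 or 120 mg BID neither named strength gives three tablets. Patients at 120 mg on 60 mg tablets, the more natural choice, score about 67% to 70%.

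Two further points are fair. The formula is consistent with its own section, so this is a conflict between sections rather than a slip in calculation. And counting held days as planned intake is a defensible definition of compliance, so that point is separate from the contradiction and the 14 days is only an illustration.

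The consequence is limited too. The study is descriptive with one treatment group, and a reader could consult the missed-dose listing, the achieved-dose table and the reasons for dose changes. Those outputs do not correct a compliance table that is wrong by construction.

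**Conclusion.** The point holds. Applied as written, Section 7.3.3 gives a wrong compliance value for any patient whose dose is not three tablets, and a wrong day-1 term for all patients. The result at 30 mg BID is exact: 33.3% for perfect intake, whatever the treatment length. At other doses the score for perfect intake runs from about 34% (60 mg BID, 60 mg tablets from Week 3) to about 195% (180 mg BID, 30 mg tablets throughout), depending on the assumed titration path and switch date. It is close to correct at 90 mg BID on 30 mg tablets and at 180 mg BID on 60 mg tablets. The error in the pooled summary depends on the mix of doses and strengths, which the SAP does not give.

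No endpoint, cut-off or analysis set uses compliance. The damage is confined to one summary and one listing, but this is the only summary statistic planned to show adherence. It should be fixed before the tables are programmed.

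**What to change.** Express compliance in milligrams:

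- **Numerator:** the sum over dispensing records of (tablets dispensed − tablets returned) × tablet strength in mg.
- **Denominator:** the sum over days of prescribed mg, that is one 30 mg dose on day 1 and then twice the recorded dose level, following its dose changes.
- Multiply the ratio by 100. Delete the statements of 3 and 6 tablets.
- State whether approved dose holds are excluded from the denominator. Excluding them is recommended if the aim is to measure adherence to what was prescribed.

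Check at 30 mg BID for 350 days: 699 × 30 mg taken over 699 × 30 mg prescribed = 100%.

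The cost is SAP wording and programming. Section 7.3.1 shows that dispensing and return data and dose by visit from Week 5 will be available. It must be confirmed that the eCRF holds bottle strength, dose-change dates in Weeks 1–4 and the dates of holds.

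If the early dose-change dates are not recorded, report compliance from Week 5 only, using the recorded dose at each visit and the bottle strength. That fallback also needs each return linked to the visit at which the bottle was dispensed. Bottles go out "At designated visits (i.e. Weeks 1, 3, 5, 9, 13, 17, 21, 26, 30, 34, 38, 42 and 46"), the SAP says only that "Patients will return the bottles at a subsequent study visit, as instructed", and each supply lasts "until the next visit plus an additional 8 tablets to allow for visit windows". Tablets from the Week 3 supply returned later must therefore not be subtracted from the Week 5 supply.

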2.2. Secondary Objectives

The secondary objectives of the study are:

- To evaluate the safety of nalbuphine by achieved maintenance dose at the end of Treatment Week 4,
- To assess skin lesion improvement using the metrics of the Prurigo Activity Score (PAS),
- Change from Baseline in Patient-Reported Outcome (PRO) measures Worst (i.e. most severe itching over the past 24 hours) itch Numerical Rating Scale (NRS), average itch intensity NRS, Verbal Rating Scale (VRS) (itchy, burning and stinging), Medical Outcomes Scale (MOS) Sleep-R, ItchyQol, and Hospital Anxiety and Depression Score (HADS) by the final Treatment Period Visit,
- Change between Baseline and the final Treatment Period Visit in Patient Benefit Index, pruritus version (PBI-P),
- A description of the percentage of patients utilizing various doses of nalbuphine HCl ER tablets by Study Week,
- A description of the frequency and reasons for dose up-and down-titration and treatment discontinuation during the study,

- Frequency and distribution by time on study of patients determined to meet failure-to-improve criteria,
- Changes in the PRO measurements during the Washout Period after cessation of treatment of nalbuphine HCl ER tablets,
- Time to first use of rescue medications and the number of days of use of rescue medications for itching,
- To evaluate the daily changes in the Subjective Opiate Withdrawal Scale (SOWS) during the Washout Period after cessation of treatment of nalbuphine HCl ER tablets.

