3.1. Overall Study Design and Plan

This is an open label safety and tolerability extension study for patients who have completed the TR03 study. Patients will either enter directly into a drug Treatment Period (Worst Itch NRS ≥ 5) or enter an extended screening period of a no-drug Observation Period (Worst Itch NRS < 5) based on their reported NRS scores on the first Visit (Visit 1a). For up to 12 extended screening weeks, patients in the no-drug Observation Period may also transition into the drug Treatment Period if their Worst Itch NRS increases to ≥ 5 .

To allow for various starting levels of pruritus intensity, patients who have a Worst Itch NRS that is ≥ 5 will enter the Treatment Period upon completion of Visit 1a. Patients whose Worst Itch NRS score is < 5 will be entered into an extended screening period, no-treatment criteria Observation Period for up to 12 weeks or until they develop a higher level of pruritus (i.e., Worst Itch NRS ≥ 5), at which point they will transition to the Treatment Period upon completion of Visit 1b. All patients entering the Treatment Period, whether immediately upon study entry or following a period of time in the Observation Period, will initially be titrated to a dose that can be as high as 180 mg twice daily (BID) during the first 4 weeks of the Treatment Period. Patients who continue in the Observation Period and maintain a Worst Itch NRS score of < 5 will be screen failed from the study at the end of the 12-week period. For enrolled patients whose Visit 1a worst itch NRS score satisfies the ≥ 5 enrollment criterion and for whom treatment is initiated, the screening visit Visit 1a will also be designated as the baseline visit. For enrolled patients who must continue into the Observation Period, the first visit during that period when the worst itch NRS ≥ 5 criterion is satisfied will be designated as Visit 1b and that visit will serve as the baseline visit.

The total study duration for any individual patient will be up to 53 weeks. For patients who enter directly into the Treatment Period, the total amount of time on drug will not exceed 50 weeks. Patients who enter the Treatment Period from the Observation Period, the total amount of time spent in the combined two periods of the study cannot exceed 50 weeks. All patients who received drug treatment will have a 2-week Washout and Safety Follow-up period at the end of the dosing period, unless consent is withdrawn.

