The total amount of time in the Observation Period cannot exceed 12 weeks. After these 12 extended screening weeks, patients not eligible for the Treatment Period are screen failed from the study. The study periods are summarized below.

Study Period	Study Weeks	Duration
Observation Period	
Patients who do not meet the criteria to start Treatment are followed in Observation Period visits (OV) for up to 12 extended screening weeks. During this time, the patient may meet criteria and become eligible to enter the Treatment Period. If the patient does not meet the criteria to enter the Treatment Period by the end of 12 extended screening weeks (OV12), participation in the study ends and the patient is screen failed
	Up to 12 Extended Screening weeks
Treatment Period	
For patients directly entering the Treatment Period as of Visit 1a, the Treatment Period begins with Study Week 1 (Visit 1a) and ends with Study Week 50.
 
For patients entering the Treatment Period after being followed in the Observation Period, the number of weeks on treatment and the end of the Treatment Period varies. (See Table 8 in the study protocol for the details of which treatment visits are to take place).
 
The End of Treatment Visit will take place after the patient completes the last week of study drug.
	Up to 50 weeks
Washout and Safety Follow-Up Period	
The Washout and Safety Follow-up Period is two (2) weeks in duration.
 
For patients directly entering the Treatment Period as of Visit 1a and completing 50 weeks of study drug treatment, the Washout and Safety Follow-up Period should take place during weeks 51 and 52.
 
For patients entering the Treatment Period after being followed in the Observation Period, the number of weeks on treatment and the end of the Treatment Period varies; Table 8 in the Study Protocol calculates the Treatment Visit assignments for any patient entering the Treatment Period from the respective Observation Period visits. The Washout and Safety Follow-up Period will take place during the two (2) weeks after the patient completes the last week of study drug.
 
The Washout and Safety Follow-up Period Visit will take place in the week following the completion of the two (2) week Washout and Safety Follow-up Period.
	2 weeks

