3.2. Premature Discontinuation of Study Drug Treatment

3.2.1. Premature Discontinuation of Study Drug Treatment Associated with Failure-to-Improve Criterion

Patients who meet failure-to-improve criterion during the conduct of the study, will stop taking study medication.

The Failure-to-Improve criteria are as follows: Beginning on Treatment Period Visit 3 (TV3), and at every subsequent Treatment visit, patients with a worst itch NRS score \geq the worst itch NRS score at Visit 1a (or at Visit 1b in the case of patients who require the OV period) will be discontinued from study drug. Patients discontinued from study drug are to undergo the End of Treatment Visit (TV14), the Washout/Safety Follow-up Period assessment in two weeks, and receive a follow-up telephone contact 30 days following end of study drug dosing for final safety assessment.

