8.1.3. Change from Baseline in the VRS

The VRS scale to be used in this study has three dimensions, each dimension is coded with graduated adjectives (from 0 = none; to 5 = very severe) for the skin sensations of itchy, burning and stinging. Patients will be asked to record the VRS value: “How is your skin sensation today?”

Summaries of each of the three skin sensations will be presented as detailed in Section [8.1](#). In addition, for each of the three skin sensations, patients’ change between baseline and LOV will be summarized using frequencies and percentages for the following categories: 4 grades better, 3 grades better, 2 grades better, 1 grade better, no change (VRS change of $< \text{abs}(1)$), 1 grade worse, 2 grades worse, 3 grades worse and 4 grades worse. The summary will be presented for all patients, patients with at least 6 months of treatment, patients with at least 9 months of treatment and patients who have completed the treatment period. Patients will be counted in each treatment duration category whose criteria they have met (i.e. A patient who has completed the treatment period will be included in the denominator for all patients, patients with at least 6 months of treatment, patients with at least 9 months of treatment and patients who have completed the treatment period.).

All VRS data will be presented in a data listing for the safety population.

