8.1.5. Change from Baseline in the ItchyQoL

The ItchyQoL consists of 22 pruritus-specific items measuring how pruritus affects patients' QOL in the area of symptoms related to the itch condition (6 questions), functional limitations (7

questions), and emotions (9 questions). The subject scores each question never =1, rarely=2, sometimes=3, often=4 and all the time=5.

Individual scores for each of the 22 items will be summarized categorically using frequencies and percentages at each study visit.

The ItchyQoL total score will be obtained as the sum of the 22 items. If no more than three items are missing, each missing item will be estimated as the mean of the remaining items. If more than three items are missing, the ItchyQoL total score will be set to missing.

Summaries for ItchyQoL total score will be presented as detailed in Section [8.1](#). In addition, change in ItchyQoL total score between baseline and LOV will be summarized using frequencies and percentages for the following categories: very good improvement, marked improvement, some improvement, no change, slightly worse, markedly worse and much worse. The magnitude of ItchyQoL change associated with each category is taken from [Siebenhaar et al., 2013](#): Very good improvement: > 50% to 100% reduction; Marked improvement: > 20% to 50% reduction; Some improvement: > 5% to 20% reduction; No change: 5% reduction to 5% increase; Slightly worse: > 5% to 20% increase; Markedly worse: > 20% to 50% increase; Much worse: > 50% increase. The summary will be presented for all patients, patients with at least 6 months of treatment, patients with at least 9 months of treatment and patients who have completed the treatment period. Patients will be counted in each treatment duration category whose criteria they have met (i.e. A patient who has completed the treatment period will be included in the denominator for all patients, patients with at least 6 months of treatment, patients with at least 9 months of treatment and patients who have completed the treatment period.).

Individual ItchyQoL item scores as well as the calculated total score for each patient will be presented in a data listing for the safety population.

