8.1.8. Change from Baseline in PAS

The PAS consists of 7 qualitative and quantitative measurements related to the examination of the skin. Type, number, distribution, affected body parts, and quantitative number of lesions in a representative body part are documented. The biggest lesion and the most representative lesion are monitored with documentation of height and area measurements. Prurigo lesion activity is recorded as a percentage based on their stage (0-4).

Separate activity classification is provided for prurigo lesions with excoriations/crusts compared to all prurigo lesions and for healed prurigo lesions compared to all prurigo lesions. The proportion of patients with each stage of classification will be summarized at each visit for each of the two activity classifications (note that PAS is not completed at the Washout/Safety and Follow-up visit). Shift from baseline to LOV and the End of Treatment visit for all patients, patients with at least 6 months of treatment, patients with at least 9 months of treatment and patients who complete treatment will also be presented for each of the two activity classifications. Shift from baseline to Visit 5/Week 13, Visit 8/Week 26 and Visit 11/Week 38 for all patients will also be presented for each of the two activity classifications.

Classification is provided for total number of prurigo lesions (not including scars). The proportion of patients at each classification level (0, 1-19, 20-100 and >100) will be summarized at each visit (note that PAS is not completed at the Washout/Safety and Follow-up visit). Shift from baseline to LOV and the End of Treatment visit for all patients, patients with at least 6

months of treatment, patients with at least 9 months of treatment and patients who complete treatment will also be presented. Shift from baseline to Visit 5/Week 13, Visit 8/Week 26 and Visit 11/Week 38 for all patients will also be summarized.

All PAS data obtained in the study will be presented in a data listing for the safety population

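### LOV includes the off-drug Washout visit, so the VRS grade-change and ItchyQoL improvement-category tables, specified only at LOV, have no on-treatment version

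*SAP*

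**What the plan says.** The LOV rule is in the opening text of SAP Section 8: "Last observed value (LOV) is defined as the values at the last post-baseline visit, up to and including the Safety and Washout Period visit". Section 8.1 applies LOV to every PRO, as a column beside the Treatment Period visits and the Washout and Safety Follow-up visit.

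Two tables rest on LOV alone:
- Section 8.1.3, for each VRS sensation: "change between baseline and LOV will be summarized using frequencies and percentages for the following categories".
- Section 8.1.5: "change in ItchyQoL total score between baseline and LOV will be summarized using frequencies and percentages".

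Both are presented for all patients, for those with at least 6 or at least 9 months of treatment, and for those who completed the treatment period.

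The objective in Section 2.2 ends its list of PRO measures with "Hospital Anxiety and Depression Score (HADS) by the final Treatment Period Visit". Section 3.3.2 words the endpoint as change by Treatment Period study visit and makes change during Washout a separate endpoint, which Section 8.2 analyses.

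For the lesion score, Section 8.1.8 says: "note that PAS is not completed at the Washout/Safety and Follow-up visit". Its shift tables are given to both LOV and the End of Treatment visit.

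**The concern.** A last-observed-value summary split by months of treatment invites the reading that it shows how patients were doing at the end of treatment. Under this definition it mostly shows how they were doing after stopping. The two category tables are the only place where the SAP classifies each patient's VRS or ItchyQoL change from baseline as better, unchanged or worse. If itch returns off drug, they would show less benefit than patients had on treatment. If patients start other antipruritic treatment after stopping, they could show more.

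The label also changes meaning. Between endpoints, LOV is off drug for most PROs but not for PAS. Within one endpoint, it is off drug for those who attend Washout and a Treatment Period value for those who do not.

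**Working it through.** The SAP states no figure to reproduce. The check follows the LOV rule through the visit schedule.

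**1. Who reaches the Washout visit.** Section 3.1 sets the rule for everyone treated, namely those "who received drug treatment will have a 2-week Washout and Safety Follow-up period at the end of the dosing period, unless consent is withdrawn". Section 3.2.1 sends patients who meet the failure-to-improve criterion there too: "Patients discontinued from study drug are to undergo the End of Treatment Visit (TV14), the Washout/Safety Follow-up Period assessment in two weeks". Section 3.2.2 asks the same of other early discontinuers. Attendance is therefore the planned route for every treated patient.

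**2. What is measured there.** Section 8.2 lists worst and average itch NRS, VRS, ItchyQoL total, MOS Sleep Question 2 and HADS. Section 8.1.6 tabulates MOS Sleep Question 1 at visits up to and including Washout, which implies that it is asked there. PAS is not done (Section 8.1.8). PBI-P is completed only before and at the end of treatment (Section 8.1.7).

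**3. How long off drug.** Section 3.1 gives the timing: "The Washout and Safety Follow-up Period Visit will take place in the week following the completion of the two (2) week Washout". With the Section 9.1 day counts for completers, which fit a full 50 weeks:
- last treatment day = first dose + 349
- washout = first dose + 350 to + 363 (14 days)
- Washout visit, in the next week = first dose + 364 to + 370
- days since last treatment day = 364 − 349 = 15 to 370 − 349 = 21

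For a failure-to-improve discontinuer, Section 3.2.1 implies about 14 days or more. NRS covers the prior 24 hours (Section 8.1.1) and VRS asks about today (Section 8.1.3), so neither score includes any time on drug. The SAP gives no recall period for ItchyQoL or HADS.

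**4. What LOV becomes.**

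| Measure | LOV if Washout attended | LOV if Washout missed | On-treatment version of the same summary? |
|---|---|---|---|
| NRS, HADS, VRS and ItchyQoL summary statistics | Washout value | last Treatment Period value | yes, by visit (8.1) |
| MOS Sleep Questions 1 and 2 | Washout value (Question 1 if asked) | last Treatment Period value | yes, by visit (8.1.6) |
| VRS grade-change table | Washout value | last Treatment Period value | **no** |
| ItchyQoL category table | Washout value | last Treatment Period value | **no** |
| PAS shifts | Treatment Period value | Treatment Period value | yes, End of Treatment (8.1.8) |

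**5. Illustration only.** The SAP gives neither Washout attendance nor any rate of return off drug. Let a share f attend, let attenders lose a share r of their on-treatment change, and let mean on-treatment change be equal in attenders and non-attenders. The mean change at LOV then shrinks by f × r:
- 0.7 × 0.25 = 17.5%
- 0.9 × 0.5 = 45%
- 0.9 × 1 = 90%
- zero if r = 0; a gain if r is negative

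For one patient, an assumed ItchyQoL total of 80 at baseline and 56 at end of treatment is a reduction of 24/80 = 30%, in the marked-improvement band (over 20% to 50%). With half the gain lost the score is 68, a reduction of 12/80 = 15%, in the some-improvement band (over 5% to 20%). A patient can thus change category without any change in on-treatment response.

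**The case against.** The definition is explicit, and the label does not claim to be on treatment. Section 8.1 reports every PRO at each Treatment Period visit with Washout beside LOV, and Section 8.2 reports the change from End of Treatment to Washout. A careful reader can therefore see any loss of benefit on the continuous scales. The two category tables are introduced as additions to those summaries. Efficacy is secondary and descriptive, there is one open-label group, no testing is planned, and the primary endpoint is the incidence of TEAEs.

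Most of this stands, and it limits the point. A reader might infer that on-treatment NRS and HADS results are lost; they are not, since only the LOV column is affected. A reader might also treat the category tables as the main responder analysis. The SAP defines no responder and ranks no efficacy table above another. Nor can one conclude that benefit will be understated: the SAP has no data on return of itch, and bias in the other direction is possible.

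What the objection does not answer is that patient-level categories cannot be rebuilt from visit means or from the mean change in Section 8.2. Openly stating the LOV rule also does not align these tables with the Section 2.2 objective. The PAS tables show that giving both time points was considered feasible.

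**Conclusion.** The point holds in limited form and should be fixed. For each patient who attends Washout, LOV for the PROs collected there is a value about two to three weeks off drug and duplicates a column already planned. The substantive gap is the VRS grade-change and ItchyQoL category tables, which are framed by treatment duration but have no on-treatment counterpart. That departs from the objective of change by the final Treatment Period Visit.

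The conclusion rests on the SAP's own schedule and on treated patients generally attending Washout as planned; the share who do is not given. The 15 to 21 days apply to a 50-week completer seen on schedule. The size and direction of the effect on the reported percentages are unknown. No test, error rate or primary safety result is affected.

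**What to change.** Redefine LOV in Section 8 as the last non-missing post-baseline value at a Treatment Period visit, up to and including TV14/End of Treatment. Keep Washout as its own column in the Section 8.1 tables and in Section 8.2. LOV would then have the same meaning for PAS and the PROs, and for a 50-week completer the time off drug at LOV would fall from about 15 to 21 days to roughly the gap between last dose and TV14.

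If the sponsor prefers to keep the present LOV, the minimum is to add End of Treatment versions of the VRS grade-change and ItchyQoL category tables, as Section 8.1.8 does for PAS, and to footnote every LOV column as including off-drug Washout values. In that case, state whether an early discontinuer's TV14 assessment counts as End of Treatment, because Section 4.1 assigns early-termination data to the next scheduled visit.

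The first option costs one sentence and one derivation flag; the second costs two further tables and a footnote. Both use only data already collected.
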